15.3 Informed Consent Process

The site investigator will ensure the subject is given full and adequate oral and written information about the nature, purpose, possible risks and benefits of the study. Subjects must also be notified they are free to discontinue from the study at any time. The subject should be given the opportunity to ask questions and allowed time to consider the information provided.

The subject's signed and dated informed consent must be obtained before conducting any procedure specifically for the study. The site investigator must store the original, signed informed consent form. A copy of the signed informed consent form must be given to the subject.

APPENDIX 1: ECOG PERFORMANCE STATUS

ECOG Score	Performance Status
0	Asymptomatic
1	Symptomatic, fully ambulatory
2	Symptomatic, in bed < 50% of the day
3	Symptomatic, in bed > 50% of the day but not bedridden
4	Bedridden
5	Dead

APPENDIX 2: DRUG INTERACTIONS WITH ENTRECTINIB

Because of the potential for drug interactions, entrectinib should be administered with caution with the drugs listed in the tables below.

Cytochrome P450 CYP3A4 Inhibitors and Inducers

Inhibitors	Inducers
Strong: Boceprevir, clarithromycin, conivaptan, grapefruit juice, indinavir, itraconazole, ketoconazole, lopinavir/ritonavir, mibefradil, nefazodone, nefazodone, nelfinavir, posaconazole, ritonavir, saquinavir, telaprevir, telithromycin, voriconazole Moderate: Aprepitant, cimetidine, ciprofloxacin, clotrimazole, crizotinib, cyclosporine, dronedarone, erythromycin, fluconazole, fluvoxamine, imatinib, tofisopam, verapamil	Strong: Alfentanil, cyclosporine, dihydroergotamine, ergotamine, fentanyl, pimozide, quinidine, sirolimus, tacrolimus, rifampin, St. John's Wort Moderate: Bosentan, efavirenz, etravirine, modafinil

Cytochrome P450 Substrates

	Sensitive Substrates	Substrates with Narrow Therapeutic Range
CYP2C9 Substrates	Celecoxib	Warfarin
CYP2D6 Substrates	Atomoxetine, desipramine, dextromethorphan, metoprolol, nebivolol, perphenazine, tolterodine, venlafaxine	Thioridazine, pimozide
CYP3A Substrates	Alfentanil, aprepitant, budesonide, buspirone, conivaptan, darifenacin, darunavir, dasatinib, dronedarone, eletriptan, eplerenone, everolimus, felodipine, indinavir, fluticasone, lopinavir, lovastatin, lurasidone, maraviroc, midazolam, nisoldipine, quetiapine, saquinavir, sildenafil, simvastatin, sirolimus, tolvaptan, tipranavir, triazolam, ticagrelor, vardenafil	Alfentanil, cyclosporine, dihydroergotamine, ergotamine, fentanyl, pimozide, quinidine, sirolimus, tacrolimus

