5.6.2 Permitted Concomitant Therapy Requiring Caution

Entrectinib is mainly eliminated through hepatic clearance and CYP3A4 plays a significant role in the biotransformation of entrectinib. Co-administration of strong or moderate CYP3A4 inhibitors and inducers should be avoided. In vitro, entrectinib exhibited potential to inhibit and induce the activities of CYP3A, and potential for inhibition of CYP2C9 and CYP2D6, which suggests a potential for interaction with other drugs metabolized by these isoforms. Because of this, entrectinib should be administered with caution with the drugs listed in Appendix 2.

In addition, since absorption of entrectinib is pH sensitive, patients using H2-receptor antagonists, proton pump inhibitors (PPIs), and/or antacids should discontinue these drugs prior to starting entrectinib. If not possible, or if after discontinuation such therapy needs to be resumed, patients should be instructed to take only H2 receptor antagonists or antacids, if possible, as the duration of action of these drugs is relatively transient compared with PPIs that have longer half-lives, and thus may be administered at safe intervals in relation to entrectinib. These medications should be taken at a time point that is not proximal to entrectinib administration (at least 3-4 hours before or after entrectinib administration).

Medications that prolong QT/QTc interval should be avoided. Subjects that require medications that prolong QT/QTc interval should be monitored closely during treatment.

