5.6.3 Prohibited Medications

Subjects are prohibited from receiving the following therapies during the Screening and Treatment Phase of this trial:

- Anti-cancer systemic chemotherapy or biological therapy not specified in this protocol
- Concomitant use of chemotherapy
- Investigational agents other than entrectinib or PAC-1
- Radiation therapy
- Herbal medications (e.g., St. John's Wort)

Subjects who, in the assessment by the investigator, require the use of any of the aforementioned treatments for clinical management, but not for progressive disease, should be removed from the trial and replaced.

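### Section 5.6.2 and Appendix 2 give two unreconciled instructions for CYP3A4 inhibitors and inducers, and the strong-inducer list needs checking against its source

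*Combined protocol and SAP*

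**What the plan says.** Section 5.6.2, headed "5.6.2 Permitted Concomitant Therapy Requiring Caution", states that "Co-administration of strong or moderate CYP3A4 inhibitors and inducers should be avoided". One sentence on entrectinib's in vitro effects on CYP3A, CYP2C9 and CYP2D6 follows, and then: "Because of this, entrectinib should be administered with caution with the drugs listed in Appendix 2".

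Appendix 2 opens by saying that "entrectinib should be administered with caution with the drugs listed in the tables below". Its first table lists strong and moderate CYP3A4 inhibitors and inducers; its second lists CYP2C9, CYP2D6 and CYP3A substrates.

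Three entries in the first table matter here:

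- The strong-inducer cell begins "Alfentanil, cyclosporine, dihydroergotamine, ergotamine, fentanyl, pimozide, quinidine, sirolimus, tacrolimus, rifampin" and ends with St. John's Wort.
- The moderate-inhibitor list begins "Aprepitant, cimetidine, ciprofloxacin, clotrimazole, crizotinib, cyclosporine, dronedarone, erythromycin", so it includes cyclosporine.
- Grapefruit juice is listed as a strong inhibitor.

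Elsewhere, Section 5.6.3 prohibits "Herbal medications" and gives St. John's Wort as its example. Section 5.7 tells patients to avoid grapefruit and its juice during treatment. Section 5.5.1 permits concomitant medication in general, but makes that permission subject to the specific prohibitions that follow it.

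**The concern.** Sites decide on co-medication from these sections. Section 5.6.2 itself says that CYP3A4 is important in the metabolism of entrectinib, so these are operative instructions that bear on patient safety. As the text stands, two sites could each follow the protocol and handle the same co-medication differently.

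The consequences also differ. Under Section 5.6.3, a subject who needs a prohibited therapy for reasons other than progression is to come off the trial and be replaced. A with-caution listing has no such consequence.

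Phase 1b is where uneven handling would be hardest to absorb. Cohorts have 3 to 6 subjects, and Section 5.1.1 lets a dose pass with at most 1 of 6 subjects having a DLT. The PK comparisons in Section 8.1.1.1 use the same few subjects, and that section names no adjustment for co-medication.

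**Working it through.** The plan states no figure on this point, so the check is a comparison of texts and lists.

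**Step 1: instructions side by side.**

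| Item | Instruction in the body | Instruction in Appendix 2 |
|---|---|---|
| Strong or moderate CYP3A4 inhibitors and inducers | Avoid, then caution by reference to Appendix 2 (both in 5.6.2) | Caution |
| St. John's Wort (strong inducer) | Prohibited (5.6.3) | Caution |
| Grapefruit juice (strong inhibitor) | Avoid (5.7) | Caution |

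The Appendix 2 lead-in speaks of tables in the plural, so it covers the inhibitor and inducer table as well as the substrate table. Every drug in the first table is therefore under both avoid and caution.

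**Step 2: strong inducers against narrow-range CYP3A substrates.** The strong-inducer cell has 11 entries. The cell for CYP3A substrates with a narrow therapeutic range has 9. Entries 1 to 9 of the first are identical to entries 1 to 9 of the second, in the same order. The remainder is 11 − 9 = 2 entries, rifampin and St. John's Wort.

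A fault in reading the PDF is an unlikely cause. The nine names run straight on into the last two, and they also appear complete in their own cell.

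**Step 3: drugs in both the inhibitor and the inducer columns.** There is exactly one, cyclosporine (moderate inhibitor and strong inducer). Of the nine repeated names, 9 − 1 = 8 have no opposing class within the documents. Separately, nefazodone appears twice among the strong inhibitors, a small sign that the table was not proofread.

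**Step 4: what the strong-inducer cell changes in practice.** Cyclosporine comes under the same Section 5.6.2 instruction in either class, because strong and moderate inhibitors and inducers are treated alike there. The other eight would carry only caution as substrates; their listing as strong inducers adds avoid. Which instruction governs those eight thus depends on whether the cell is right.

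**The case against.** The best defence is that avoid and caution address different things. The phrase that introduces the caution follows the sentence on entrectinib's effect on other drugs. Avoid could therefore cover drugs that change entrectinib exposure, and caution could cover substrates that entrectinib may affect. That may have been the intention, but the text does not limit caution to substrates: the Appendix 2 lead-in applies it to both tables.

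A second defence is tiering: avoid where possible, otherwise use caution. Section 5.6.2 does write that pattern out for QT-prolonging drugs (avoid, but monitor closely if needed) and for acid reducers (stop, or if that is not possible, separate the doses). It states no such tier for CYP3A4 drugs, so the reader has to supply it.

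On St. John's Wort, a reader might infer that the protocol leaves its status open. That goes too far. Section 5.5.1 puts specific prohibitions above the general permission, and Section 5.6.3 names the product. What stands is that Appendix 2 still lists it among drugs to be used with caution.

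A reader might also infer that nine drugs are misclassified. The documents do not support that, because inducer and substrate are not exclusive classes. Appendix 2 itself lists conivaptan, indinavir, saquinavir, aprepitant and dronedarone as both inhibitors and CYP3A substrates. Whether the other eight drugs are inducers needs an outside source.

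Finally, Section 5.5 sends co-medication questions to the sponsor-investigator and Section 5.5.1 requires all medications to be recorded. Both reduce the practical risk, but neither resolves the conflict in the text.

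**Conclusion.** The text is wrong as written, at minor severity. Three things are established:

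- CYP3A4 inhibitors and inducers carry two instructions with no stated relation between them.
- Two named items, St. John's Wort and grapefruit juice, are treated differently in the body and in the appendix.
- The strong-inducer cell repeats a nine-name substrate list in order, and cyclosporine appears under opposing classes.

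That the list was copied by mistake is a reasonable inference from the identical order, not a demonstrated fact.

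A reader might go further and conclude that DLT counts or the PK results will be distorted. One subject is 1/6 = 17% of a six-subject cohort, but that is only arithmetic on cohort size. The documents give neither the expected use of these drugs nor the size of any exposure change, so no effect is shown. Sample size, power and type I error do not depend on this text.

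The conclusion rests on the wording and the list comparison alone. It takes no view on the pharmacology of any drug or on which instruction is correct.

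**What to change.** Reconcile Sections 5.6.2, 5.6.3 and 5.7 with Appendix 2 so that each drug class, and each item named in more than one place, carries a single instruction. If two levels are intended for CYP3A4 inhibitors and inducers, state when each applies, as Section 5.6.2 already does for QT-prolonging drugs and acid reducers. Align the Appendix 2 lead-in with the outcome, for example by giving each table its own lead-in.

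Have clinical pharmacology check the strong-inducer cell against its source, with attention to the nine repeated names and to cyclosporine in particular, and remove the duplicate nefazodone entry. The documents do not settle which instruction or which entry is right, so those decisions belong to the sponsor-investigator and clinical pharmacology.

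The cost is an edit to one appendix table and a few sentences. Nothing in the statistical design or the analysis changes.
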